**Category 2: Any findings from studies that suggests a significant human risk**

The sponsor shall report any findings from other epidemiological studies, analyses of adverse events within the current study or pooled analysis across clinical studies or animal or *in vitro* testing (e.g. mutagenicity, teratogenicity, carcinogenicity) that suggest a significant risk in

humans exposed to the drug that would result in a safety-related change in the protocol, informed consent, investigator brochure or package insert or other aspects of the overall conduct of the study.

The IND sponsor must notify the FDA within 15 calendar days; unexpected fatal or immediately life-threatening suspected adverse reaction(s) shall be reported as soon as possible or within 7 calendar days.

### **12.5.3 Reporting of Adverse Events to IRB**

All investigators shall report adverse events, including expedited reports, in a timely fashion to their IRB in accordance with applicable regulations and guidelines.

## **12.6 Pregnancy Reporting**

The investigator shall be informed immediately of any pregnancy in a study subject or a partner of a study subject. A pregnant subject shall be instructed to stop taking study medication. The investigator shall counsel the subject and discuss the risks of continuing with the pregnancy and the possible effects on the fetus. Monitoring of the pregnant subject shall continue until the conclusion of the pregnancy.

The investigator shall report to the DAIT/NIAID all pregnancies within 1 business day of becoming aware of the event using the Pregnancy paper CRF. All pregnancies identified during the study shall be followed to conclusion and the outcome of each must be reported. The Pregnancy paper CRF shall be updated and submitted to the DAIT/NIAID when details about the outcome are available. When possible, similar information shall be obtained for a pregnancy occurring in a partner of a study subject.

Information requested about the delivery shall include:

- Gestational age at delivery
- Birth weight, length, and head circumference
- Gender
- Appearance, pulse, grimace, activity, and respiration (APGAR) score at 1 minute, 5 minutes, and 24 hours after birth, if available
- Any abnormalities.

All pregnancy complications that result in a congenital abnormality, birth defect, miscarriage, and medically indicated abortion - an SAE shall be submitted to the IND Sponsor and to DAIT/NIAID using the SAE reporting procedures described above.

## **12.7 Reporting of Other Safety Information**

An investigator shall promptly notify the site IRB as well as the DAIT/NIAID, when an “unanticipated problem involving risks to subjects or others” is identified, which is not otherwise reportable as an adverse event.

## **12.8 Review of Safety Information**

### **12.8.1 Medical Monitor Review**

The DAIT/NIAID Medical Officer shall receive periodic reports from the protocol investigator compiling new and accumulating information on AEs, SAEs, and pregnancies recorded by the study site(s) on appropriate paper CRFs.

The Medical Officer shall review and make decisions on the disposition of the SAE and pregnancy reports received by the protocol investigator (See Sections 12.5.1, *Reporting of Serious Adverse Events to Sponsor*, and 12.6, *Pregnancy Reporting*).

Additionally, the Independent Medical Monitor who is a physician who is independent from the study team and will, at minimum, review all SAEs to assess for possible changes to the overall risk of the study. This person will be expected to communicate with the Protocol Chair/Principal Investigator and the NIAID Medical Officer regarding any safety issues and may be requested to review study safety documentation.

## 12.8.2 DSMB Review

### 12.8.2.1 Planned DSMB Reviews

The Data and Safety Monitoring Board (DSMB) shall review safety data at least yearly during planned DSMB Data Review Meetings. Data for the planned safety reviews will include, at a minimum, a listing of all reported AEs and SAEs.

The DSMB will be informed of an Expedited Safety Report in a timely manner.

### 12.8.2.2 Ad hoc DSMB Reviews

In addition to the pre-scheduled data reviews and planned safety monitoring, the DSMB may be called upon for *ad hoc* reviews. The DSMB will review any event that potentially impacts safety at the request of the protocol chair or DAIT/NIAID. In addition, any study stopping rule that is met will trigger an *ad hoc* comprehensive DSMB Safety Review:

After review of the data, the DSMB will make recommendations regarding study conduct and/or continuation.

#### 12.8.2.2.1 Temporary Suspension of enrollment for *ad hoc* DSMB Safety Review

- Any participant develops a severe asthma exacerbation that requires treatment in the emergency room, hospitalization, or the use of systemic steroids, at any time during the study. A temporary halt in enrollment will be implemented if an *ad hoc* DSMB safety review is required.

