### 11.2. Participant Stopping Rules and Withdrawal Criteria

Participants may be prematurely terminated from the study for the following reasons:

1. The participant elects to withdraw consent from all future study activities, including follow-up.
2. The participant is "lost to follow-up" (i.e., no further follow-up is possible because attempts to reestablish contact with the participant have failed).
3. The participant dies.
4. The Investigator no longer believes participation is in the best interest of the participant.
5. Individual safety stopping rules:
  - a. The participant develops a medical condition or is started on new medication(s) that, in the opinion of the investigator, may pose additional risks from participation in the study, may interfere with the participant's ability to comply with study requirements or that may impact the quality of the data obtained from the study.
  - b. A severe asthma exacerbation that requires treatment in the emergency room, hospitalization, or the use of systemic steroids, at any time during the study.
  - c. Use of a required but excluded medication such as inhaled corticosteroids or leukotriene modifiers.
  - d. Non-adherence to study procedures. Patients who miss visit 3 or 4 may be permitted to remain in the study as long as they comply with all other visits.
  - e. Pregnancy
  - f. Positive CoVID-19 test

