### 11.5. Study Stopping Rules

The enrollment and dosing of RV-16 in the study may be suspended pending review by the NIAID DSMB and the University of Virginia IRB for the following reasons:

- Any subject has a severe asthma exacerbation that requires treatment in the emergency room or hospitalization
- $\geq 2$  subjects experience severe asthma exacerbations requiring oral corticosteroids for  $\geq 5$  days, pending further expedited review.
- Any subject treated for pneumonia
- Any subject dies until expedited review is completed to determine whether the death might have resulted from any of the study procedures.
- Complications post biopsy requiring an urgent care visit in  $\geq 2$  subjects.
- Any death that occurs in the study, which is possibly or definitely related to study treatment regimen.
- The occurrence of a Grade 3 or higher related SAE in 2 or more of the study participants who have received a study treatment.

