## **Appendix 1: Treatment Guidelines for Asthma Symptom Exacerbations**

### **Treatment guidelines should symptom exacerbations occur during the study:**

If a study participant experiences an increase in lower respiratory tract symptoms, or a decline in lung function, the following plan describes how subjects will be treated.

- For FEV1 value dropping between 20-29%20% from the baseline value not responding to albuterol, start on inhaled corticosteroids (Flovent 110 mcg./puff, 2 puffs bid) and discontinue when symptoms return to baseline.
- For FEV1 value dropping between 30- 49% from the baseline value not responding to albuterol, check oximetry and start on inhaled corticosteroid as above and 3 to 5 days of oral steroids (Prednisone 50 mg/day).
- For FEV1value dropping 50% or more from the baseline value. Transportation to the emergency room will be recommended and arranged. Individual stopping rules will apply as described in the Complete Clinical Protocol (Section 8.1.2). Further follow-up and management with the subject's primary care doctor; [name] and his study team will continue to be involved and available for follow-up and evaluation 30 days afterward for any subject who requires oral steroids, a visit to the ER, or hospital admission.

These treatment plans are in keeping with recommendations from the *Guidelines for the Diagnosis and Management of Asthma* (60).

**Note:** Baseline FEV1 values apply to the FEV1 measurements established at the scheduled visit with 2 days of RV-16 inoculation. Also note that young adults rarely become febrile during a natural or experimental infection with rhinovirus. However, if subjects develop a temperature greater than or equal to 101 degrees F, [name], together with back-up from the allergy fellow on call will be contacted (paged) for evaluation.\

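### For severe asthma exacerbations treated with systemic steroids alone, sections 11.5 and 12.8.2.2.1 set conflicting study-level suspension triggers, and 3- or 4-day oral courses never count under 11.5's steroid rule

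*Combined protocol and SAP*

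**What the plan says.** **Section 12.8.2.2.1** (temporary suspension of enrollment for ad hoc DSMB review) lists a single event: "Any participant develops a severe asthma exacerbation that requires treatment in the emergency room, hospitalization, or the use of systemic steroids". It needs one participant and sets no minimum course. It then adds: "A temporary halt in enrollment will be implemented if an" ad hoc DSMB review is required.

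**Section 11.5**, repeated in the synopsis, opens: "The enrollment and dosing of RV-16 in the study may be suspended pending review by the NIAID DSMB" and the IRB. Its first bullet reads: "Any subject has a severe asthma exacerbation that requires treatment in the emergency room or hospitalization". Steroids are not mentioned there. They appear only in the second bullet, which requires 2 or more subjects and reads "subjects experience severe asthma exacerbations requiring oral corticosteroids for" 5 days or more.

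**Section 12.8.2.2** links the two: "any study stopping rule that is met will trigger an" ad hoc DSMB review. It also lets the protocol chair or DAIT/NIAID request a review of any event that may affect safety.

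**Appendix 1** gives "3 to 5 days of oral steroids" for one band of FEV1 decline. Section 5.3 gives the same range of days.

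**Section 11.2** has an individual rule in nearly the same words as 12.8.2.2.1: "A severe asthma exacerbation that requires treatment in the emergency room, hospitalization, or the use of systemic steroids, at any time during the study". It concerns the withdrawal of that participant, not the study.

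**The concern.** Every participant is deliberately infected, and the study-level rules decide when the next person may be enrolled or inoculated. Among past asthmatic challenges at this site, section 1.3 reports one oral-steroid case in 45 and no emergency room visit or hospital admission. The exacerbation treated with steroids alone is therefore the event with a precedent, and it is the one on which the sections part. Section 5.1 also accepts that including well-controlled asthmatics on inhaled corticosteroids could lead to more severe exacerbations, and relies on the existing safety monitoring criteria to suffice.

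When the first such case occurs, the site finds it listed as a suspension event in one section and short of the threshold in another. Whether a second case counts under 11.5 then depends on whether each course ran to 5 days, a length that varies within the protocol's own treatment range.

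**Working it through.** The plan states no operating characteristics for its stopping rules, so there is no figure to reproduce. The check compares the texts and then illustrates the size of the gap.

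**Step 1. The two rules for a severe exacerbation treated with steroids alone**

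| Element | 11.5 and synopsis | 12.8.2.2.1 |
|---|---|---|
| Count | at least 2 subjects | 1 participant |
| Qualifying treatment | oral corticosteroids, at least 5 days | any systemic steroid, no minimum |
| Scope | enrollment and dosing | enrollment |
| Verb | may be suspended | will be halted, if a review is required |
| Review body | DSMB and IRB | DSMB |

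For emergency room treatment or hospitalization, both act on one subject. The conflict is confined to steroid-only cases.

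**Step 2. Course length.** Appendix 1 and section 5.3 allow 3, 4 or 5 days. Only 5 meets a minimum of 5, so 3- and 4-day courses never satisfy the 11.5 steroid bullet, however many occur. The one past oral-steroid course in section 1.3 lasted 5 days and would have counted.

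**Step 3. The condition in 12.8.2.2.1.** The halt applies if an ad hoc review is required. Under 12.8.2.2 a review follows automatically when a stopping rule is met; otherwise it is by request.
- If only the 11.5 rules count as stopping rules, the steroid wording in 12.8.2.2.1 has no automatic effect.
- If that wording is itself a trigger, it conflicts with the two-subject, 5-day rule.

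Both readings need a change of text.

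**Step 4. Illustration.** Inputs:
- n = 20 asthmatics (section 3.1).
- p, the rate of steroid-treated exacerbations: 1/45 (section 1.3) or 1/23 (section 5.1, GMP RV-39 pool). p = 0.10 is added as an assumption.
- q, the share of courses reaching 5 days: assumed 1, 0.5 or 0. Put r = p × q.

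Formulas, with events independent across participants:
- At least one event: 1 − (1 − p)^20
- At least two events with 5-day courses: 1 − (1 − r)^20 − 20r(1 − r)^19

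For p = 1/45 and q = 1: at least one is 1 − (44/45)^20 = 0.362. Exactly one is 20 × (1/45) × (44/45)^19 = 0.290. At least two is 0.362 − 0.290 = 0.072.

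| p | One event, any course | Two events, q = 1 | Two events, q = 0.5 | Two events, q = 0 |
|---|---|---|---|---|
| 1/45 | 0.362 | 0.072 | 0.021 | 0 |
| 1/23 | 0.589 | 0.215 | 0.069 | 0 |
| 0.10 (assumed) | 0.878 | 0.608 | 0.264 | 0 |

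**Step 5. Uncertainty.** The exact 95% interval for 1 in 45 is 0.06% to 11.8%. Over that range the chance of at least one event runs from 0.01 to 0.92, and of at least two (q = 1) from below 0.001 to 0.70.

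**The case against.** The strongest reply is that these are two tiers. Section 12.8.2.2.1 is a sensitive pause on enrollment; 11.5 is a wider suspension of enrollment and dosing that also involves the IRB. The distinction has practical content: section 8.4 places Visit 1 between 5 and 28 days before inoculation, so someone enrolled but not yet inoculated could be affected by one rule and not the other. Both rules are in force, and since 11.5 only permits suspension, acting on 12.8.2.2.1 breaches neither.

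What stands is that the actions differ and that a tiered design is possible. But the protocol never says that it has tiers, and the circular condition described above leaves the lower tier without a clear automatic trigger.

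Three stronger readings are tempting, and the documents do not support them:
- *The safety boundary is undefined, and steroid-treated cases could accumulate unchecked.* The sections agree at one subject for emergency room treatment or hospitalization. The other 11.5 triggers remain (pneumonia, death, biopsy complications, Grade 3 or higher related SAEs in 2 or more participants). Systemic steroid treatment is a recorded adverse event under 12.2.1, individual withdrawal applies under 11.2, and a review can be requested.
- *One steroid-treated case definitely halts the study.* Section 12.8.2.2.1 concerns enrollment only, and its halt is conditional.
- *Courses under Appendix 1 never count.* A 5-day course does.

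**Conclusion.** The concern holds for severe exacerbations treated with systemic steroids alone. The study-level trigger is one participant with any course in 12.8.2.2.1, and two subjects with at least 5 days each in 11.5 and the synopsis. Scope and verb differ as well, and nothing states how the rules relate. It is a contradiction in a safety decision rule, and worth an amendment even though other safeguards exist.

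The probabilities only show that the choice of rule matters: 0.36 against 0.07 at 1/45, and 0.59 against 0.22 at 1/23, when every course lasts 5 days. They should not be read as forecasts. Both rates rest on one past case, read here as the same one in sections 1.3 and 5.1, which followed RV-39 and not the RV-16 used here. The calculation also assumes independent events, counts only the asthma cohort, and treats every steroid-treated exacerbation as severe under both sections. The two-event figures describe the 11.5 steroid bullet alone; they do not bound the chance of suspension under 11.5 as a whole.

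**What to change.** Reconcile the synopsis, 11.5, 12.8.2.2, 12.8.2.2.1 and Appendix 1 in one of two ways:

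- **One rule:** a single count, a single definition of a qualifying steroid course that is explicit about the course lengths in Appendix 1 and section 5.3, a single scope (enrollment, or enrollment and dosing) and a single verb (may or will).
- **Two declared tiers:** state that they are tiers, what triggers each, what each suspends, and how one leads to the other.

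In either case, remove the circular condition in 12.8.2.2.1 by saying outright whether the listed event itself requires the ad hoc review. The threshold is for the sponsor and DSMB to set; this review does not propose one.

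The cost is a protocol amendment with notice to the DSMB and IRB. Depending on the threshold chosen, the chance of a temporary halt will also change, and that trade-off should be put to the DSMB openly.

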## 13. Statistical Considerations and Analytical Plan

### 13.1 Overview

**Objectives:** Our primary objective will be to address the hypothesis that epigenetic changes selectively develop in nasal epithelial cells (EC) during the evolution of allergic airway disease as a result of which nasal EC are programmed to produce cytokines central to orchestrating an allergic inflammatory immune response in the upper – and lower – airways. We will determine whether nasal epithelium from allergic asthmatics and rhinitics when infected with RV, is programmed to secrete cytokines that promote a Th2 cytokine “signature” (IL-25, IL-33, and TSLP) as well as mediators directly driving engagement of an allergic inflammatory process (including CCL5, CCL11, CXCL1, and GMCSF). A total of 60 subjects will be enrolled including 20 each that are normal controls, allergic rhinitis controls, and asthmatics. Cytokine/chemokine will be collected at day 0, 1, 2, 3, 4, and 7 post-infection and evaluated by qPCR and EIA.

We will correlate the expression of these cytokines with engagement of an allergic inflammatory response, including eosinophil co-recruitment at days 1-4. In addition, we predict that in asthma and AR systemic increases in eosinophilia will be observed, but that only in asthmatics will increased asthma symptoms, bronchial hyperreactivity, and eNO be observed.

**Analytical approach:** The RV challenge model is an example of a serial study design, in which subjects will receive a nasal presentation of RV-16 on challenge day 0 and then they will be serially monitored in the CRU for 7 days. **Analytical method selection:** Due to the fact that most of our data collection will be serial in nature, i.e. data will be collected on challenge days 0, 1, 2, 3, 4, and 7, the analytical methods that we select to use to analyze our primary and secondary outcome data will take into account the *repeated measure* aspect of the RV challenge model. **Missing data:** We will make a concrete effort to limit the occurrence of missing data, and if deemed necessary, multiple-imputation methods will be utilized to control biases associated with incomplete data. **Levels of detection:** If specimen levels are below the level of assay detection, we will use the mid-point between 0 and the minimum detection level of the assay as the unit of analysis.

### 13.2 Outcomes

- IL-25, IL-33, TSLP qPCR in nasal scraping-derived specimens (days 1-7)
- IL-25, IL-33, TSLP protein in nasal sponge-derived specimens (days 1-7)
- Th2 immune deviating activity in nasal sponge-derived specimens (days 1-7)
- Upper and lower respiratory symptoms via ACT and questionnaire (days 1-7)
- FEV1 (days 1-7)
- FeNO (days 1-7)
- Circulating AEC (day 4)
- Bronchial hyperreactivity (methacholine PD20) (day 4)
- RV load in nasal secretions (qPCR) (days 1-7)
- IFN- $\alpha$ ,  $\beta$ -,  $\lambda$  and IL-15 by qPCR (days 1-7)
- Nasal biopsy samples (day 4) will be evaluate for % of infected cells and amongst the cells whether they display evidence of apoptosis (annexin V positive) or necrosis (PI positive).

### 13.3 Measures to Minimize Bias

N/A

### Analysis Plan

#### 13.4.1 Analysis Populations.

Normal control subjects, allergic rhinitis controls, and asthmatics

#### 13.4.2 Primary Analysis of Primary Endpoint(s)/Outcome(s)

**Analysis of RV-induced IL-25 expression:** The endpoint data will be the challenge study day 0, 1, 2, 3, 4, and 7 nasal scraping derived measurements of IL-25 qPCR expression. **Endpoint transformations:** Since we expect that the IL-25 expression measurements on any particular challenge study day (i.e. day 0, 1, 2, 3, 4, and 7) will be distributed approximately Log-Normal (positive skewed distribution), we will transform the IL-25 expression data to the natural logarithmic scale.

**Units of analysis:** The day 0  $\log_e$ (IL-25 qPCR expression) measurements will be subtracted from the post-challenge day 1, 2, 3, 4, and 7  $\log_e$ (IL-25 qPCR expression) measurements and these *subject-specific* pre- versus post-challenge changes in  $\log_e$ (IL-25 qPCR expression) will be the units of analysis. **Analytical approach:** The changes in  $\log_e$ (IL-25 qPCR expression) on post-challenge days 1, 2, 3, 4, and 7 will be analyzed as repeated measures by way of a linear mixed model (LMM). **LMM fixed effects:** Two sources of variability in the pre- versus post-challenge changes in  $\log_e$ (IL-25 qPCR expression) will be of primary interest. One source of variability will be the study-group to study-group variability (i.e. asthmatics, allergic rhinitis controls, and healthy-controls) in the changes in  $\log_e$ (IL-25 qPCR expression), while the other source of variability will be the post-challenge day to day variability in the changes in  $\log_e$ (IL-25 qPCR expression). **Concomitant variable variability:** Variability in the  $\log_e$ (IL-25 qPCR expression) changes due to inherent differences in day 0  $\log_e$ (IL-25 qPCR expression) will be extracted from the residual error to increase statistical power. **Random effects:** *Subject-specific* and *time-specific* random effects will be incorporated into the LMM to allow *intra-subject* measurement correlation to be accounted for in variance estimation and hypothesis testing. **Hypothesis testing:** *Between-study-group comparisons:* With regard to hypothesis testing, the pivotal comparisons will be the *between* study-group comparisons of the mean changes in  $\log_e$ (IL-25 qPCR expression) on post-challenge study days 3 and 4 when cold symptoms are expected to peak. More specifically, we will compare if the study-day 3 and study-day 4 mean changes in  $\log_e$ (IL-25 qPCR expression) differ between the 3 different underlying study-populations after taking into account the inherent variability in challenge study-day 0  $\log_e$ (IL-25 qPCR expression). These comparisons will require conducting a total of 6 hypothesis tests (i.e. 3 per study day), and in order to maintain an *intraday* experimental-type I error rate of 0.05, the null hypothesis rejection rule for the “*intraday*” *between-group* comparisons will be based on a Bonferroni corrected two-sided  $p \leq 0.0167$  (i.e.  $0.05/3$ ) rejection rule. *Within-study-group comparisons:* On a per *study-group* basis, we will conduct statistical tests to determine if the means of the  $\log_e$ (IL-25 qPCR expression) distributions on post-challenge days 1, 2, 3, 4, and 7, differ from the mean of the  $\log_e$ (cytokine expression) distribution on challenge study day 0. The *within-study-group* comparisons will be considered *secondary* in nature, and this set of comparisons will be primarily focused on the challenge study-day 3 and challenge study-day 4 changes in mean  $\log_e$ (IL-25 qPCR expression) when symptoms are expected to peak. More specifically, we will test if the mean of the  $\log_e$ (IL-25 qPCR expression) distribution is the same on challenge study-day 0 and challenge study-day 3 and if the mean of the  $\log_e$ (IL-25 qPCR expression) distribution is the same on challenge study-day 0 and challenge study-day 4. A Bonferroni corrected two-sided  $p \leq 0.025$  (i.e.  $0.05/2$ ) decision rule will be utilized as the null hypothesis rejection criterion for this set of tests. **Confidence intervals:** To aid in data interpretation, a 95% confidence interval will be constructed for each *between-group* comparison and for each *within-group* comparison. **Scale of interpretation:** The point-estimate and the lower and the upper 95% confidence interval limits will be anti-log transformed so that point-estimate and the lower and the upper limits of the 95% confidence interval represent ratios of geometric mean cytokine expression. **Alternative analytical approach:** If the linear mixed model assumptions are deemed to be violated for this endpoint, we will use a linear mixed model based permutation test strategy to derive empirical based *distribution free* tests for testing the aforementioned *between-group* and *within-group* hypotheses.

**Analysis of RV-induced lower-respiratory symptoms:** The lower respiratory symptom scores from challenge study-days 0, 1, 2, 3, 4, and 7, will be analyzed in two different ways. In the first approach; due to the expected infrequency of lower respiratory symptoms in the allergic rhinitis and healthy control cohorts, cumulative lower respiratory total symptom (CLRTS) will be computed for challenge period; day 0 to day 4, and for challenge period; day 0 to day 7. In the second approach the daily total lower respiratory symptom scores will be analyzed.

**Analytical approach #1:** We will use the total lower respiratory symptom scores of challenge days 0, 1, 2, 3, and 4 to compute to a cumulative lower respiratory symptom score (CLRTS) for challenge period day 0 to day 4, and we will use the total lower respiratory symptom scores of challenge days 0, 1, 2, 3, 4, and 7 to compute a CLRTS for challenge period day 0 to day 7. **Analytical approach:** The CLRTS will be analyzed as integer scaled random variables by way of a Negative Binomial (NB) generalized estimating equation (GEE) model. **GEE model specification:** The GEE model specification for the CLRTS analysis will include two predictor variables. One predictor variable will identify the study-group (i.e. asthmatics, allergic rhinitis controls, and healthy-controls) while the other predictor variable will identify the challenge period (i.e. day 0 to day 4, or day 0 to day 7). **Variance estimation:** An “unstructured” variance-covariance matrix form will be utilized to account for the inherent correlation between the first set of CLRTS scores (challenge day 0 to challenge day 4) and the second set of CLRTS scores (challenge day 0 to challenge day 7). **Hypothesis testing:** Wald tests will be conducted to determine if the means of CLRTS distributions for each challenge period differ from study-population to study populations. A Bonferroni two-sided  $p \leq 0.0167$  (0.05/3) criterion will be utilized as the null hypothesis rejection rule for the intra-challenge-period, between-group comparisons.

**Analytical approach #2:** We will analyze the lower respiratory total symptom scores for challenge days 0, 1, 2, 3, 4, and 7 as repeated measures in this approach. **Analytical approach:** The lower respiratory total symptom score data will be analyzed by way of a negative-binomial generalized estimating equation (GEE) model. **Model specification:** The GEE model specification will include two predictor variables. One predictor variable will identify the study-group (i.e. asthmatics, allergic rhinitis controls, and healthy-controls), while the other predictor variable will identify the challenge study-day (i.e. day 0, 1, 2, 3, 4, or 7). **Variance estimation:** A “working independence” variance covariance matrix form will be utilized to account for the inherent *intra-subject* measurement correlation induced by the repeated measures aspect of the RV challenge study design. **Hypothesis testing:** Wald chi-square tests will be utilized to test if the means of total lower symptom score distributions on a particular challenge day differed between the 3 different study-groups. The primary focus will be to determine if the means of total lower symptom score distributions differed between the 3 different study-groups on study-days 3 and 4, when symptoms are expected to peak.

**Analysis of the severity of RV-induced infection:** The post-challenge (i.e. challenge days 1 to 7) RV loads in the nasal secretions of challenged subjects will be derived via qPCR. Quantification is based upon serial dilutions of a standardized pool of the virus with a known TCID50/ml. **Data transformation:** Since the RV load data will be quantified in terms of “virion frequency per unit volume of nasal section”, it is expected that based on previous RV challenge studies that the RV load data will have to be analyzed on the log10 scale. **Analytical approach:** The nasal secretion RV load data will be analyzed via a LMM. **Model specification:** Two sources of nasal secretion RV load variability will be examined. One source of variability will be the study-group to study group variability (i.e. asthmatics, allergic rhinitis controls, healthy-controls) and the other source of variability will be the post-challenge day to day variability (i.e. challenge day 1, 2, 3, 4, or 7). **Hypothesis testing:** The pivotal *between-group* comparisons will be focused on the post-challenge day 3 and day 4 nasal secretion RV loads when symptoms are expected to peak. Post-challenge day 3 and day 4 mean log10(nasal secretion RV load) will be compared in a pairwise manner between the 3 different study-populations. In order to maintain an *intraday* experimental type I error rate 0.05, a Bonferroni corrected two-sided  $p \leq 0.05/3$  decision rule will be utilized as the null hypothesis rejection rule.

Post-challenge day 1, 2, and 7 *between-group* comparisons of mean  $\log_{10}$ (nasal secretion RV load) will be considered as secondary comparisons and the same hypothesis testing procedures will be employed to conduct these *between-group* comparisons. *Within-group* related hypotheses will also be considered as secondary hypotheses. ***Scale of interpretation:*** The point estimates and 95% confidence interval limits for the *between-group* and the *within-group* comparisons of mean  $\log_{10}$ (RV load) will be anti-log transformed so that the *between-group* comparisons and the *within-group* comparisons of nasal secretion RV load can be interpreted as ratios of “nasal secretion RV load” geometric means.

